4.2.a	Narrative Study Description	
Participants will be randomly assigned to a Congruent or Incongruent Structure Group. The intervention consists of a missing feature task in Stage 1 in which each participant learns a novel category whose structure is determined by their assigned group. In Stage 2, we will use another missing feature task to expose participants to a new category whose structure is identical to the category learned by the Congruent group in Stage 1. We will assess the effect of our intervention by comparing accuracy on the missing feature task across groups in Stage 2. Our planned sample size of <math>N=100</math> results in statistical analyses with <math>N=50</math> which is sufficient to detect our expected effects.
	
Aim 2 includes Stage 1, a delay, and Stage 2. Participants are assigned to different experimental conditions such that some participants learn only Lattice categories in Stage 1 (Incongruent) while others are exposed to a Modular category (Congruent). Participants are also assigned to Awake or Sleep groups. Categories in Stage 1 are paired with different auditory tones to be used later in TMR in the sleep groups. All participants learn a new Modular category in Stage 2. The Awake participants (Incongruent and Congruent) remain awake during the 2 hour delay between Stage 1 and 2. Sleep participants are given a nap opportunity during the delay while sleep stages are monitored with EEG. For participants who learned a Modular as well as a Lattice category in Phase 1, TMR will be used to selectively activate the Lattice (Incongruent) or Modular (Congruent) category. Participants in the Sleep Control group learned two Lattice categories in Phase 1 one of which will be reactivated with TMR. We will assess the effect of our intervention by comparing missing feature task accuracy in Stage 2 across groups. Accounting for an expected 20% attrition rate in the sleep groups, we plan to collect data from 173 participants, resulting in a final planned sample size of <math>N=150</math>. This results in statistical analyses with <math>N=30</math> which is sufficient to detect our expected effects, based on previous studies using these methods.

4.2.b	Primary Purpose	Basic Science	Basic Science
4.2.c	Interventions		
	Intervention Type	Behavioral	Behavioral

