	Name	Learning either a Modular or Lattice category in Phase 1	Awake vs. Sleep, Lattice vs. Modular category in Phase 1, and TMR for either abstract Modular or Lattice structure during the sleep period
	Description	Participants will either learn a Modular or a Lattice category in Phase 1. Then all participants will learn a new Modular category in Phase 2. Ability to learn the new Modular category will be assessed to determine effect of intervention.	The Awake vs. Sleep intervention determines whether participants remain awake or take a nap during the delay period. The Lattice vs. Modular intervention determines whether participants learn two Lattice categories in Phase 1, or one Lattice and one Modular category. The TMR intervention determines whether TMR is used to reactive a Lattice or Modular category during the nap session. After the delay, ability to learn a new Modular category in Phase 2 will be assessed to determine effect of interventions.
4.2.d	Study Phase	Other	Other
4.2.e	Intervention Model	Parallel: Participants will either learn a Modular or a Lattice concept in Phase 1.	Parallel: Participants will be assigned to either an Awake-Congruent, Awake-Incongruent, Sleep-Congruent, Sleep-Incongruent, or Sleep-Control group.
4.2.f	Number of Arms	2	5
4.2.g	Masking	Participant, investigator	Participant
	Allocation	Randomized	Randomized
	Enrollment	100	173
4.3 Outcome Measures			
4.3	Name	Structure knowledge for a new Modular category in Stage 2.	Structure knowledge for a new Modular category in Stage 2.
	Type	Accuracy	Accuracy
	Time Frame	Final accuracy is collected in a missing feature task which occurs 25 minutes after the experiment begins and takes 25 minutes to complete. Stage 1 and Stage 2 will take 50 minutes to complete.	Final accuracy is collected in a missing feature task which occurs 2 hours and 50 minutes after the experiment begins and takes 25 minutes to complete. Stage 1, Stage 2, and the intervening delay period will take 3 hours and 15 minutes to complete.
	Brief Description	The outcome measure is accuracy (0-100%) on the missing feature task in Stage 2.	The outcome measure is accuracy (0-100%) on the missing feature task in Stage 2.
4.4 Statistical Design and Power			
	# of subjects	100	150
	Expected effect size	0.85	0.85
	Power	0.98	0.85

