## **Statistical Analysis Plan**

For Aim 1, the outcome measure is accuracy (0-100%) on the missing feature task for the Modular category in Stage 2. The statistical method we will use to assess this outcome measure will be a two-sample t-test to compare accuracy on the new Modular category in Stage 2 across groups (Congruent vs. Incongruent).

For Aim 2, the outcome measure is accuracy (0-100%) on the missing feature task for the Modular category in Stage 2. The statistical method we will use to assess this outcome measure will be a two-sample t-test to compare accuracy across groups (Congruent vs. Incongruent, Awake vs. Sleep).

Our statistical methods are appropriate given comparable research on category learning and structure learning.

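### Aim 2: the Incongruent label means different Stage 1 exposure in the Awake and Sleep arms, and the SAP does not say which arms its Awake vs. Sleep t-test compares

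*SAP*

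**What the plan says.** The SAP's Aim 2 paragraph gives the analysis as a "two-sample t-test to compare accuracy across groups (Congruent vs. Incongruent, Awake vs. Sleep"). It gives factor labels, not arms. Sleep-Control does not appear in the SAP text available for review.

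Protocol 4.2.a (Aim 2) uses the labels in two ways:

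- **By Stage 1 exposure:** "some participants learn only Lattice categories in Stage 1 (Incongruent) while others are exposed to a Modular category (Congruent").
- **By TMR target, among sleepers:** "For participants who learned a Modular as well as a Lattice category in Phase 1", the text continues, "TMR will be used to selectively activate the Lattice (Incongruent) or Modular (Congruent) category".

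Of the Awake arms it says "The Awake participants (Incongruent and Congruent) remain awake during the 2 hour delay between Stage 1 and 2". Of the fifth arm it says "Participants in the Sleep Control group learned two Lattice categories in Phase 1 one of which will be reactivated with TMR".

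Protocol 4.2.c treats exposure as a factor separate from TMR: "The Lattice vs. Modular intervention determines whether participants learn two Lattice categories in Phase 1, or one Lattice and one Modular category". Protocol 4.2.e lists five arms, and 4.4 describes a t-test with 30 per group.

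**The concern.** TMR is described only for the nap, so the exposure definition is the only one that can apply to the Awake arms. Awake-Incongruent has therefore had no Modular category. Sleep-Incongruent has had one, and differs from Sleep-Congruent only in which category is cued. The sleep arm whose Stage 1 exposure matches Awake-Incongruent is Sleep-Control.

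This matters because the Aim 2 objective in Protocol 4.1 is the contribution of sleep, and Awake vs. Sleep is the only sleep-wake comparison the SAP names. Earlier Modular learning is what Aim 1 studies as a cause of better Stage 2 performance on a new Modular category. If it does help, a comparison with more Modular exposure on the sleep side can show an apparent sleep benefit that is partly or wholly exposure.

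Matched and mismatched pairs both fit the SAP wording, so the choice could be made after the results are known. The Congruent vs. Incongruent comparison shifts in the same way: it is an exposure contrast among Awake participants and a TMR-target contrast among sleepers.

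**Working it through.** **1. Does the sample size count Sleep-Control?** Protocol 4.2.a says "Accounting for an expected 20% attrition rate in the sleep groups, we plan to collect data from 173 participants", for 150 analysed. Two Awake arms of 30 give 60. Three sleep arms of 30 give 90, and 90/0.8 = 112.5. The total is 60 + 112.5 = 172.5, rounded up to 173, so the stated figure reproduces. With two sleep arms it would be 60 + 60/0.8 = 135. Sleep-Control is therefore in the enrolment.

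**2. Arms side by side (Protocol 4.2.a, 4.2.c, 4.2.e).**

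| Arm | Modular in Stage 1 | Delay | TMR target |
|---|---|---|---|
| Awake-Congruent | yes | wake | none described |
| Awake-Incongruent | no | wake | none described |
| Sleep-Congruent | yes | nap | Modular |
| Sleep-Incongruent | yes | nap | Lattice |
| Sleep-Control | no | nap | Lattice |

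**3. Exposure imbalance under each reading of Awake vs. Sleep.** Let e be the effect of Modular exposure on Stage 2 accuracy, in SD units. The difference due to exposure alone is e × (share exposed in Sleep − share exposed in Awake).

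| Reading | n (Awake vs Sleep) | Shares (Awake, Sleep) | Exposure difference |
|---|---|---|---|
| Congruent pair | 30 vs 30 | 100%, 100% | 0 |
| Awake-Incongruent vs Sleep-Control (label read by exposure) | 30 vs 30 | 0%, 0% | 0 |
| Incongruent pair by arm name | 30 vs 30 | 0%, 100% | e |
| Four labelled arms pooled | 60 vs 60 | 50%, 100% | e/2 |
| All sleep arms pooled | 60 vs 90 | 50%, 67% | e/6 |

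The 30 per group in Protocol 4.4 points away from pooling. It fits all three 30 vs 30 rows and does not choose among them.

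**4. Illustrative rejection rates.** Assumptions: no sleep or TMR effect; within-arm SD 1; pooled-variance t-test; two-sided 0.05 (no level is stated); e = 0.85, 0.5 or 0.2. Protocol 4.4 gives 0.85 as the expected effect size but ties it to no contrast, so it serves only as the top of a range.

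- *30 vs 30, mismatched.* The noncentrality is e/√(1/30 + 1/30). For e = 0.85 this is 3.29 against a critical value of 2.00 on 58 df, so rejection is 0.899. For e = 0.5 (1.94) it is 0.478, and for e = 0.2 (0.77) it is 0.119.
- *60 vs 60.* Mixing two Awake arms with different means inflates that group's variance to about 1 + e²/4. At e = 0.85 that is 1.18, and the average with 1 is 1.09. The critical difference is 1.98 × √(1.09 × 2/60) = 0.378. The actual difference is 0.425 with standard error √(2/60) = 0.183, so rejection is Φ((0.425 − 0.378)/0.183), about 0.60. Simulation gives 0.604, 0.264 and 0.083 for the three values of e.
- *60 vs 90.* Simulation gives 0.102, 0.070 and 0.053.
- *Exposure-matched pairs.* 0.05 throughout.

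**5. Power of a 30 vs 30 contrast at 0.85 SD.** The same formula gives 0.899 at two-sided 0.05. Protocol 4.4 states 0.85. The difference does not affect this point.

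**The case against.** The strongest reply is that the SAP never says it will compare Awake with Sleep within Incongruent. That stands. A reader might infer that the mismatched pair is the planned test, especially from the arm names and the 30 per group. But 30 per group fits the Congruent pair equally well. If the label is read by exposure, as Protocol 4.2.c describes the factor, Sleep-Control becomes the natural partner for Awake-Incongruent. The documents support only that the contrast is unspecified and that one natural pairing, and both pooled ones, are unbalanced.

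A second reply concerns the matched pairs. A reader might infer that they give an unbiased estimate of sleep, so that the SAP wording is the only problem. That goes too far. Every sleep arm receives TMR and no Awake arm is described as receiving it, so the matched pairs still combine nap and TMR. With no effect of sleep itself, an assumed Modular TMR benefit of 0.2 or 0.5 SD would make Sleep-Congruent vs Awake-Congruent reject 12% or 48% of the time.

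Third, 90% is the top of the range, not a forecast. It needs the full 0.85 SD to be an exposure effect that survives the delay, with no effect of Lattice TMR. If Lattice TMR lowered performance by an assumed 0.25 or 0.425 SD, 90% would fall to 63% or 37%.

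Finally, part of the SAP was not available, so silence on Sleep-Control refers to the text that was. The double use of the label in Protocol 4.2.a stands regardless.

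**Conclusion.** The concern holds as one of specification and should be fixed before analysis. The change of meaning between Awake-Incongruent and Sleep-Incongruent is clear from Protocol 4.2.a. The available SAP text analyses by those labels without naming arms, and leaves out an arm that the enrolment counts.

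The exposure imbalance is 100 percentage points in the Incongruent pair by arm name, 50 when the four labelled arms are pooled, and about 17 when Sleep-Control is added to the pool. Under the stated assumptions, rejection with no sleep or TMR effect is about 90%, 48% or 12% for the mismatched pair; 60%, 26% or 8% for 60 vs 60; and 10%, 7% or 5% for 60 vs 90. The size of the exposure effect is not known from the documents, and a non-zero TMR effect would change every one of these figures, including the 5% for matched pairs.

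It does not follow that the planned test is certainly confounded by exposure, or that correcting the wording isolates sleep.

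**What to change.** Replace the Aim 2 sentence in the SAP with named arm pairs:

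- **Sleep-wake:** Sleep-Congruent vs Awake-Congruent, and Sleep-Control vs Awake-Incongruent. Describe each as nap with TMR against wake, because no pair of these arms separates sleep from TMR.
- **TMR target:** Sleep-Congruent vs Sleep-Incongruent.
- **Exposure:** Awake-Congruent vs Awake-Incongruent.

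State that Sleep-Incongruent vs Awake-Incongruent will not be used, alone or within a pool, as a test of sleep. State the role of Sleep-Control. In both documents, label arms by Stage 1 exposure and TMR target so that one word does not carry both. Name the primary contrast before the data are seen. How to handle multiplicity across the contrasts is a separate matter for the investigators.

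The cost is wording only: same arms, participants and data. The downside is that each sleep-wake contrast stays at 30 vs 30 and gives up a larger pooled comparison. That is the group size the protocol already plans, with stated power of 0.85 (about 0.90 on recalculation at 0.85 SD and an assumed two-sided 0.05).

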**Grant Title:** The emergence of abstract structure knowledge across learning and sleep

**NCT number:** NCT05746299

**Date:** November 11, 2021

		Aim 1	Aim 2
4.1 Brief Summary			
4.1	Brief Summary	
The objective of this study is to determine whether learning a category with a certain structure in Stage 1 improves learning of a new category with the same structure in Stage 2. The primary endpoint is accuracy on the missing feature task in Stage 2.
	
The objective of this study is to evaluate the contribution of sleep to the consolidation of abstract structural representations. The primary endpoint is accuracy in the missing feature task in Stage 2, administered after the delay period.

4.2 Study Design			

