	Statistical methods	T-test comparing accuracy between groups ( $N=50$ each group)	T-test comparing accuracy between groups ( $N=30$ each group)
4.5 Subject Participation Duration			
	Time to complete study	1 hour	3.5 hours
4.6 FDA-regulated intervention?			
	Yes/No	No	No
4.7 Dissemination Plan

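### Aim 2 does not say which of its five arms enter each of two unranked contrasts, so Awake vs Sleep pooled over the labelled arms appears to mix sleep with Stage 1 exposure; alpha and success rule are also unstated

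*SAP*

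**What the plan says.** The Aim 2 objective in protocol section 4.1 is to "evaluate the contribution of sleep to the consolidation of abstract structural representations". There is one primary endpoint, accuracy on the Stage 2 missing feature task after the delay.

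The SAP analyses it with a "two-sample t-test to compare accuracy across groups (Congruent vs. Incongruent, Awake vs. Sleep". Protocol section 4.4 adds only "T-test comparing accuracy between groups ( $N=30$ each group", an expected effect of 0.85 and power of 0.85.

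Section 4.2.e names the arms: "Awake-Congruent, Awake-Incongruent, Sleep-Congruent, Sleep-Incongruent, or Sleep-Control group". Section 4.2.c says the category intervention "determines whether participants learn two Lattice categories in Phase 1, or one Lattice and one Modular category".

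Section 4.2.a uses the label Incongruent in two ways. For Stage 1 learning: "some participants learn only Lattice categories in Stage 1 (Incongruent) while others are exposed to a Modular category (Congruent". For nappers who learned both kinds of category: "TMR will be used to selectively activate the Lattice (Incongruent) or Modular (Congruent) category". It describes Sleep-Control as having learned two Lattice categories, one of them cued during the nap.

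The available text does not rank the contrasts. It gives no alpha, sidedness, success rule or multiplicity adjustment, and does not say which arms form each side of each contrast.

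**The concern.** The SAP describes two two-level factors, but the design has five arms that do not form a clean two-by-two layout. Incongruent appears to mean different Stage 1 learning in the awake and nap arms. Pooling the four arms that carry SAP labels therefore gives an Awake vs Sleep comparison in which one of two Awake arms, but both Sleep arms, had Modular exposure. Congruent vs Incongruent has a related problem: it is a learning contrast among the awake and a cueing contrast among the nappers.

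Aim 1 is built on the idea that prior Modular learning helps Stage 2. A sleep contrast unbalanced on that exposure could suggest a sleep benefit where none exists. With the arm list open, the choice could also be made after seeing the data. Two unranked tests of one endpoint add a second, smaller question: what counts as success, and at what error rate.

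**Working it through.** **1. The plan's sample size.** Five arms of 30 give 150. With three nap arms inflated for 20% attrition: 60 + 90/0.80 = 172.5, so 173, as stated. With only two nap arms inflated: 90 + 60/0.80 = 165, which does not match. Sleep-Control is therefore a sleep group for sample size, but the SAP does not place it.

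**2. The plan's power.** Read 0.85 as a standardized mean difference (an assumption). Normal formula: power ≈ Φ(d√(n/2) − z).
- Aim 2, n = 30: 0.85 × √15 = 3.292. At two-sided 0.05, Φ(3.292 − 1.960) = 0.909 (noncentral t 0.899). At two-sided 0.025, Φ(3.292 − 2.241) = 0.853 (t 0.836). Stated: 0.85.
- Aim 1, n = 50: 0.85 × √25 = 4.25. At 0.05, 0.989; at 0.025, 0.978. Stated: 0.98.

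The level 0.025 fits the Aim 2 figure better, but no text states it. About 26 per arm, or an effect of 0.79, would also give 0.85 at 0.05. Aim 1 has a single test and also fits 0.025, so the fit does not show a planned split between two tests.

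**3. Stage 1 exposure by arm**, as sections 4.2.a and 4.2.c appear to read, with means (in SD) for an illustration in which Modular exposure alone adds 0.85 and nap and cue do nothing:

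| Arm | Stage 1 | Delay | Cue | Mean |
|---|---|---|---|---|
| Awake-Congruent | Lattice + Modular | wake | none | 0.85 |
| Awake-Incongruent | two Lattice | wake | none | 0 |
| Sleep-Congruent | Lattice + Modular | nap | Modular | 0.85 |
| Sleep-Incongruent | Lattice + Modular | nap | Lattice | 0.85 |
| Sleep-Control | two Lattice | nap | Lattice | 0 |

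**4. Awake vs Sleep under that illustration.** Simulated two-sample t-tests, 30 per arm, two-sided 0.05. There is no sleep effect, so each rejection is a false sleep finding.

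| Arms compared | Expected difference (SD) | Rejects |
|---|---|---|
| Both Awake vs Sleep-Congruent + Sleep-Incongruent (60 v 60) | 0.85 − 0.425 = 0.425 | 60% |
| Both Awake vs all three Sleep arms (60 v 90) | 1.70/3 − 0.425 = 0.142 | 10% |
| Awake-Congruent vs Sleep-Congruent (30 v 30) | 0 | 5% |
| Both Awake vs Sleep-Congruent + Sleep-Control (60 v 60) | 0 | 3.3% |

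The last figure is below 5% because each pooled side mixes two arms with different means, which enlarges the SD that the t-test uses.

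**5. Familywise error with no true differences, if either test may succeed.** For independent tests at 0.05: 1 − 0.95² = 9.75%; at 0.025: 1 − 0.975² = 4.94%. Simulation allowing for correlation:
- Two pooled contrasts: 9.7% to 9.8% at 0.05, wherever Sleep-Control goes; about 4.9% at 0.025.
- Two 30 v 30 contrasts sharing an arm: 9.1% at 0.05; 4.7% at 0.025.
- Four arm-level tests, if the N=30 row means that (an inference): 16% at 0.05; 8.6% at 0.025.
- Both pooled tests required at 0.05: 0.2% to 0.3%.

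**6. Power of the remedies**, 30 v 30, effect 0.85:
- Single primary test at 0.05: 0.90.
- Second contrast, tested at 0.05 only if the first succeeds: 0.81 (no shared arm) to 0.83 (shared arm) if both effects hold; about 0.04 if the sleep effect is null.
- Holm for two tests at overall 0.05: 0.84 at the first step (0.025); 0.88 to 0.89 per test if both effects hold.

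**The case against.** **The arms are listed.** That is right: section 4.2.e names all five, and a reader who infers that the plan leaves its arms undefined would be mistaken. Only their assignment to contrasts is missing.

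**The 10% is not the plan's error rate.** Also right. It needs two-sided 0.05 per test and a rule that either test suffices, and neither is stated. The level that fits the stated Aim 2 power better gives about 5%. The contrasts also concern different factors, and whether two such questions form one error family is debatable, particularly in a study whose stated purpose is basic science. A reader might infer that Aim 2 runs at twice its nominal error; the documents do not support that.

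**The 60% is constructed.** No text attributes 0.85 SD to exposure alone in Aim 2, and 60% belongs to the least balanced of the four groupings shown. Sleep-Control is the natural exposure match for Awake-Incongruent, and using it that way removes the inflation. So a reader should not infer a 60% chance of a false sleep finding. What stands is that the SAP does not select among these groupings, and that they can answer the sleep question differently.

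**Part of the SAP file was not available.** Statements about what is absent cover the available text only.

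**Conclusion.** The concern holds as a gap in specification and should be fixed. The main defect is the arm mapping: taken literally, the labels allow a sleep contrast confounded with Stage 1 exposure. In the exposure-only illustration, rejection runs from about 3% to 60% depending solely on which arms are chosen. This rests on the apparent reading of section 4.2.a, on 0.85 being a standardized effect, and on the assumption that exposure alone produces it.

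Multiplicity is secondary and conditional: about 10%, about 5%, or no inflation, depending on an alpha and success rule that are not stated. It is a separate defect, since adjusting for two tests would not cure the confounding. Confidence is medium.

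**What to change.** Before Aim 2 outcomes are analysed, amend the SAP as follows.

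- List the arms on each side of each contrast, including Sleep-Control, and reconcile the two uses of Incongruent.
- Match the sleep contrast on Stage 1 exposure. Examples are Awake-Congruent vs Sleep-Congruent, which tests nap plus Modular cue, or both Awake arms vs Sleep-Congruent plus Sleep-Control, which tests nap plus cue more broadly.
- State alpha and sidedness.
- Then either (1) name the sleep contrast, which addresses the stated objective, as the single primary test at two-sided 0.05 with the other contrast secondary; or (2) keep both as primary tests, either of which may succeed, with Holm at overall two-sided 0.05.
- Label further contrasts exploratory, and restate the 0.85 power for the contrasts and alpha chosen.

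The cost is SAP wording, with no extra participants. Option 1 does not reduce power for the sleep contrast, but if the second contrast is gated on it, a null sleep effect leaves that contrast almost no chance. Option 2 avoids this for a small loss at the first step (0.84 against the stated 0.85). If the chosen sleep contrast is pooled 60 v 60, power at 0.025 is 0.99 for a pooled difference of 0.85 SD but 0.52 for half that, so the restated power should say which difference is expected.
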